Potentially leading to amputation	10012679	Diabetic neuropathic ulcer
Potentially leading to amputation	10012680	Diabetic neuropathy
Potentially leading to amputation	10017711	Gangrene
Potentially leading to amputation	10020937	Hypoaesthesia
Potentially leading to amputation	10021137	Hypovolaemia
Potentially leading to amputation	10021519	Impaired healing
Potentially leading to amputation	10021784	Infected skin ulcer
Potentially leading to amputation	10022562	Intermittent claudication
Potentially leading to amputation	10024774	Localised infection
Potentially leading to amputation	10028862	Necrosis ischaemic
Potentially leading to amputation	10029331	Neuropathy peripheral
Potentially leading to amputation	10031149	Osteitis
Potentially leading to amputation	10031252	Osteomyelitis
Potentially leading to amputation	10031253	Osteomyelitis acute
Potentially leading to amputation	10031256	Osteomyelitis chronic
Potentially leading to amputation	10031262	Osteomyelitis salmonella
Potentially leading to amputation	10031264	Osteonecrosis
Potentially leading to amputation	10033775	Paraesthesia
Potentially leading to amputation	10034568	Peripheral coldness
Potentially leading to amputation	10034576	Peripheral ischaemia
Potentially leading to amputation	10034620	Peripheral sensory neuropathy
Potentially leading to amputation	10034636	Peripheral vascular disorder
Potentially leading to amputation	10036155	Poor peripheral circulation
Potentially leading to amputation	10036410	Postoperative wound infection
Potentially leading to amputation	10040026	Sensory disturbance

Statistical Analysis Plan

Version: Final 3.0
Lexicon Pharmaceuticals Protocol No. EFC14837

Date of Issue: 21 November 2019
Covance Study ID:000000155205

EOSI	Preferred Term Code	Preferred Term
Potentially leading to amputation	10040840	Skin erosion
Potentially leading to amputation	10040872	Skin infection
Potentially leading to amputation	10040943	Skin ulcer
Potentially leading to amputation	10042343	Subcutaneous abscess
Potentially leading to amputation	10043607	Thrombosis
Potentially leading to amputation	10048031	Wound dehiscence
Potentially leading to amputation	10048038	Wound infection
Potentially leading to amputation	10049927	Dry gangrene
Potentially leading to amputation	10050473	Abscess limb
Potentially leading to amputation	10050502	Neuropathic ulcer
Potentially leading to amputation	10051548	Burn infection
Potentially leading to amputation	10052428	Wound
Potentially leading to amputation	10052949	Arterial therapeutic procedure
Potentially leading to amputation	10053692	Wound complication
Potentially leading to amputation	10053716	Wound necrosis
Potentially leading to amputation	10054044	Diabetic microangiopathy
Potentially leading to amputation	10056340	Diabetic ulcer
Potentially leading to amputation	10056418	Arterial bypass operation
Potentially leading to amputation	10056673	Peripheral sensorimotor neuropathy
Potentially leading to amputation	10057518	Peripheral artery angioplasty
Potentially leading to amputation	10057525	Peripheral artery occlusion
Potentially leading to amputation	10058041	Wound sepsis
Potentially leading to amputation	10058042	Wound abscess
Potentially leading to amputation	10059245	Angiopathy
Potentially leading to amputation	10059385	Extremity necrosis
Potentially leading to amputation	10059442	Wound infection staphylococcal
Potentially leading to amputation	10059444	Wound infection pseudomonas
Potentially leading to amputation	10060734	Diabetic foot
Potentially leading to amputation	10060803	Diabetic foot infection
Potentially leading to amputation	10060963	Arterial disorder
Potentially leading to amputation	10060965	Arterial stenosis
Potentially leading to amputation	10061627	Amputation
Potentially leading to amputation	10061655	Arterial graft
Potentially leading to amputation	10061657	Arterial stent insertion

Statistical Analysis PlanVersion: Final 3.0
Lexicon Pharmaceuticals Protocol No. EFC14837Date of Issue: 21 November 2019
Covance Study ID:000000155205

EOSI	Preferred Term Code	Preferred Term
Potentially leading to amputation	10061666	Autonomic neuropathy
Potentially leading to amputation	10061815	Diabetic vascular disorder
Potentially leading to amputation	10062198	Microangiopathy
Potentially leading to amputation	10062255	Soft tissue infection
Potentially leading to amputation	10062585	Peripheral arterial occlusive disease
Potentially leading to amputation	10062599	Arterial occlusive disease
Potentially leading to amputation	10062610	Ischaemic limb pain
Potentially leading to amputation	10062932	Wound treatment
Potentially leading to amputation	10064250	Staphylococcal osteomyelitis
Potentially leading to amputation	10064601	Iliac artery occlusion
Potentially leading to amputation	10065237	Osteomyelitis bacterial
Potentially leading to amputation	10065239	Osteomyelitis fungal
Potentially leading to amputation	10065240	Wound infection bacterial
Potentially leading to amputation	10065242	Wound infection fungal
Potentially leading to amputation	10068653	Bone abscess
Potentially leading to amputation	10069379	Peripheral arterial reocclusion
Potentially leading to amputation	10072170	Skin wound
Potentially leading to amputation	10072557	Peripheral artery restenosis
Potentially leading to amputation	10072560	Peripheral endarterectomy
Potentially leading to amputation	10072561	Peripheral artery bypass
Potentially leading to amputation	10072562	Peripheral artery stent insertion
Potentially leading to amputation	10072563	Peripheral artery stenosis
Potentially leading to amputation	10072564	Peripheral artery thrombosis
Potentially leading to amputation	10074396	Penetrating atherosclerotic ulcer
Potentially leading to amputation	10075118	Subperiosteal abscess
Potentially leading to amputation	10075714	Vasculitic ulcer
Potentially leading to amputation	10076246	Spontaneous amputation

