#### **10.3.1 Temporary treatment discontinuation with investigational medicinal product**

Temporary treatment discontinuation may be considered by the Investigator because of suspected AEs.

Lower extremity complications (such as skin ulcers, infection, osteomyelitis, and gangrene) requiring treatment should lead to temporary discontinuation of IMP.

If at any visit after Randomization up to Week 8 there is a rise in creatinine level (ie, >50% increase from Baseline level, where Baseline level is defined as the mean of creatinine values obtained at Screening and Randomization) or if at any visit after Week 8 there is a rise of >50% above the mean of creatinine values from last 2 visits, the Investigator should ensure that no reasonable explanation exists for creatinine increase.

The IMP should be stopped for 2 weeks.

Reinitiating of treatment with the IMP will be done under close and appropriate clinical/and or laboratory monitoring once the Investigator has considered according to his/her best medical judgment in the occurrence of the concerned event was unlikely to be related to the IMP and if that the selection criteria for the study are still met (refer to [Section 7.1](#) and [Section 7.2](#)).

If at creatinine recheck the patient has returned to the below threshold then IMP will be restarted at a reduced dose (ie, dose reduced via IRT to 200 mg for those randomized to 400 mg; maintained at 200 mg for those randomized to 200 mg). Since the IMP received is blinded, patients must return to the site and IRT will be contacted for IMP re-initiation.

It is in the interest of the patient to monitor their blood glucose during the temporary discontinuation period, therefore regular determination of SMBG is to be performed and documented (see [Section 9.2.1.8](#)).

For all temporary treatment discontinuations, duration should be recorded by the Investigator in the appropriate pages of the e-CRF when considered as confirmed.

Temporary treatment discontinuation decided by the Investigator corresponds to more than 1 dose not administered to the patient.

Use of any other anti-hyperglycemic medication during the time of temporary treatment discontinuation (ie, insulin during a hospitalization) is to be recorded as concomitant medication with the name and dose recorded in the e-CRF.

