Renal events

For the EOSI renal events where selected events are adjudicated, the number (%) of patients with any renal events identified in [Table 3](#) in [Section 2.1.4.2](#) will be summarized by treatment group.

The following renal events will be listed along with the adjudication outcome if applicable, including events,

1. Recorded in eCRF “GFR decrease”.
2. Recorded in eCRF “Renal Event - Dialysis”.
3. Identified as “Renal transplant” in eCRF “Other procedure”.

Renal death will be part of all deaths specified above.

Other EOSIs

For EOSIs that are not adjudicated, the number (%) of patients with at least one event will be summarized by treatment group and by PT (as identified in [Table 3](#) in [Section 2.1.4.2](#)).

Severe hypoglycemia will be included in the summary of hypoglycemia (See [Section 2.4.5.1](#)).

AE leading to an amputation is described in the section below.

Analysis of Amputation

The number (%) of patients with amputation will be summarized by treatment group and by PT and LLT during the study (ie, regardless of on- or post-treatment). Amputation is a procedure recorded in eCRF “Other Procedures related to Amputation”. Patients who had a procedure related to amputation will be listed.

The number (%) of patients with an “AE leading to an amputation” will be summarized by treatment group and by PT. The “AE leading to an amputation” is determined by the AE identifier recorded in eCRF “Other Procedures related to Amputation” when “AE correction” is chosen as the reason for the amputation procedure.

In addition, the number (%) of patients with an “AE potentially leading to an amputation” will be summarized by treatment group and by PT (as identified in [Table 3](#) in [Section 2.1.4.2](#)); these PTs in [Table 3](#) were requested by the European Medicines Agency/Pharmacovigilance Risk Assessment Committee [EMA/PRAC] Assessment Report 9 February 2017). The associated list will be provided as well, with patients who had an amputation procedure flagged. “AE potentially leading to an amputation” represents the condition that may potentially lead to the amputation procedure, but not in all cases an amputation has occurred (as per the EMA/PRAC request).

Analysis of pretreatment and posttreatment adverse events

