Bladder cancer	10005007	Bladder cancer Stage 0, without cancer in situ
Bladder cancer	10005008	Bladder cancer Stage I, with cancer in situ
Bladder cancer	10005009	Bladder cancer Stage I, without cancer in situ
Bladder cancer	10005010	Bladder cancer Stage II
Bladder cancer	10005011	Bladder cancer Stage III
Bladder cancer	10005012	Bladder cancer Stage IV
Bladder cancer	10005056	Bladder neoplasm
Bladder cancer	10005075	Bladder squamous cell carcinoma recurrent
Bladder cancer	10005076	Bladder squamous cell carcinoma Stage 0
Bladder cancer	10005077	Bladder squamous cell carcinoma Stage I
Bladder cancer	10005078	Bladder squamous cell carcinoma Stage II
Bladder cancer	10005079	Bladder squamous cell carcinoma Stage III
Bladder cancer	10005080	Bladder squamous cell carcinoma Stage IV
Bladder cancer	10005081	Bladder squamous cell carcinoma stage unspecified
Bladder cancer	10005084	Bladder transitional cell carcinoma
Bladder cancer	10051690	Urinary bladder sarcoma
Bladder cancer	10057352	Metastatic carcinoma of the bladder
Bladder cancer	10066749	Bladder transitional cell carcinoma Stage 0
Bladder cancer	10066750	Bladder transitional cell carcinoma recurrent
Bladder cancer	10066751	Bladder transitional cell carcinoma Stage I
Bladder cancer	10066752	Bladder transitional cell carcinoma Stage IV
Bladder cancer	10066753	Bladder transitional cell carcinoma Stage II
Bladder cancer	10066754	Bladder transitional cell carcinoma Stage III
Bladder cancer	10071664	Bladder transitional cell carcinoma metastatic
Bladder cancer	10078341	Neuroendocrine carcinoma of the bladder
Potentially leading to amputation	10003084	Areflexia
Potentially leading to amputation	10003178	Arterial thrombosis

Statistical Analysis Plan

Version: Final 3.0
 Lexicon Pharmaceuticals Protocol No. EFC14837

Date of Issue: 21 November 2019
 Covance Study ID:000000155205

EOSI	Preferred Term Code	Preferred Term
Potentially leading to amputation	10003210	Arteriosclerosis
Potentially leading to amputation	10003222	Arteriosclerotic gangrene
Potentially leading to amputation	10006784	Burning sensation
Potentially leading to amputation	10007904	Cellulitis enterococcal
Potentially leading to amputation	10007905	Cellulitis gangrenous
Potentially leading to amputation	10007921	Cellulitis staphylococcal
Potentially leading to amputation	10007922	Cellulitis streptococcal
Potentially leading to amputation	10012174	Dehydration
Potentially leading to amputation	10012665	Diabetic gangrene

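### SAP Appendix C's list of events potentially leading to amputation counts cellulitis only when it is gangrenous or one of three organisms is named; the unqualified term is absent

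*SAP*

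**What the plan says.** SAP Table 3 identifies an AE potentially leading to an amputation by the terms in Appendix C. A footnote explains that this is not an EOSI defined in the protocol. It was added at the request of health authorities because of its relevance to lower limb complications and amputations. SAP 2.4.5.2, under the analysis of amputation, says the grouping "represents the condition that may potentially lead to the amputation procedure", attributes the terms to a European regulatory assessment report of February 2017, and plans two outputs: the number and percentage of patients by treatment group and PT, and a listing that flags patients who had an amputation procedure.

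The cellulitis terms in Appendix C are "Cellulitis enterococcal", "Cellulitis gangrenous", "Cellulitis staphylococcal" and "Cellulitis streptococcal". The same list also holds broad infection terms that name no limb, such as "Soft tissue infection".

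**The concern.** A report of cellulitis of the foot with no organism given would not obviously match any of the four listed cellulitis terms, while a skin or soft tissue infection at any body site would be counted. A wish to restrict the list to limb events therefore does not explain the gap.

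The protocol treats this kind of event as important: "Lower extremity complications (such as skin ulcers, infection, osteomyelitis, and gangrene) requiring treatment should lead to temporary discontinuation of IMP" (Protocol 10.3.1). Exclusion criterion E 37 likewise removes patients whose lower extremity complications still need treatment at randomization. What is at stake is whether one supplementary safety count, and the listing attached to it, depends on how fully the infection was described in the report.

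A side issue concerns what the total contains. Dehydration and "Hypovolaemia" are on this list and also define the volume-depletion EOSI. The grouped total could therefore rise through volume depletion without any limb event.

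**Working it through.** No sample size, power or alpha figure bears on this point. The check is a reading of the term list.

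**Step 1: read the whole list.** The rows labelled as potentially leading to amputation in Appendix C come to 97 distinct preferred terms. They run in ascending code order. Around the cellulitis rows the codes go from 10006784 (burning sensation) straight to 10007904 (the enterococcal term), with no page break or redaction between them. Nothing suggests a row lost when the file was read.

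**Step 2: compare term families within the list.**

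| Family | Terms listed | Unqualified term present? |
|---|---|---|
| Cellulitis | 4 (three organisms, one gangrenous) | No |
| Osteomyelitis | 7 | Yes |
| Wound infection | 6 | Yes |
| Gangrene | 4 | Yes |
| Skin ulcer | 2 | Yes |
| Abscess | 5 (limb, subcutaneous, wound, bone, subperiosteal) | No |
| Necrosis | 3 (ischaemic, wound, extremity) | No |

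Cellulitis differs from the four families listed in general form, but it is not the only family without a general term.

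**Step 3: see whether another rule closes the gap.** The Table 3 footnote on search terms commits only to refreshing them to the MedDRA version in effect at database lock. That does not clearly add a term that was never listed. The broad terms (skin infection, soft tissue infection, localised infection) count only events coded to those PTs.

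**Step 4: what can be said about size.** Let s be the share of cellulitis AEs coded to an unqualified term. The four listed terms then capture 1 − s. The documents give no value for s, so these are assumed values:

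- s = 0.3: 70% captured
- s = 0.5: 50% captured
- s = 0.7: 30% captured
- s = 0.9: 10% captured

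With about 260 patients planned per arm (SAP 1.1), one uncounted patient is 1/260 = 0.38 percentage points of the arm's rate.

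**Step 5: the volume-depletion overlap.** Dehydration (10012174) and hypovolaemia (10021137) carry the same codes in both Appendix C lists, so the same event is counted in both groupings.

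**The case against.** The strongest reply is that the sponsor is following a regulator's list. SAP 2.4.5.2 says the terms were requested, and the source is not in the documents. If the omission is inherited, keeping to the list is compliance, not error. That stands, and it is why the first step is a check against the source.

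The limited role of the grouping also stands. It is not a protocol EOSI, and SAP 2.4.5 calls the safety analysis essentially descriptive. The protocol EOSI, an AE leading to an amputation, is taken from the AE linked to the procedure in the eCRF with no restriction on PT, so cellulitis that led to an amputation is captured. Amputation procedures are tabulated and listed separately, and an independent blinded committee reviews amputation cases (Protocol 6.3.4). The decisions under Protocol 10.3.1 and E 37 do not use Appendix C.

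Unqualified cellulitis also remains visible by arm in the general TEAE tables by PT. This answers only part of the point. A count of patients with any listed event cannot be rebuilt by adding PT rows, because one patient may appear in several.

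On dehydration and hypovolaemia, the grouping is defined by what may lead to amputation, not by limb site, and the table by PT shows each term on its own row. That makes a separate total optional.

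**Conclusion.** The gap is real and of low severity. As written, the grouped patient count and its listing omit cellulitis that is neither gangrenous nor attributed to one of three organisms, while several comparable families are listed in general form. No efficacy result and no protocol-defined EOSI is affected.

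A reader might infer that most limb cellulitis drops out of the safety comparison. The documents do not support this. It would need s above 0.5, no coding frequencies are given, and the listed cellulitis terms name no body site. A figure of 2 to 7 patients per arm can be produced (260 × 0.01 × 0.80 = 2.1; 260 × 0.03 × 0.95 = 7.4). It rests wholly on an assumed cellulitis incidence of 1% to 3% and an assumed 80% to 95% of reports naming no organism, and it counts cellulitis at any site. Nor do the documents show whether the omission is a transcription slip or part of the regulator's request.

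One further assumption remains: that the dictionary has an unqualified cellulitis PT. The pattern of the other families suggests it, but the documents do not state it.

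**What to change.** 1. Check Appendix C against the regulator's source list, and confirm the unqualified PT in the dictionary version in use.
2. If the term was dropped in transcription, restore it.
3. If the requested list omits it, leave that list intact. Add unqualified cellulitis as a supplementary row, and show the patient-level total by arm with and without it.
4. Optionally, also show the total without dehydration and hypovolaemia, which are already counted under volume depletion.
5. Label these as additions made after the first step results were reported. SAP 1.6 states that the first step analysis was conducted and reported for top line results, so the regrouping should not be presented as planned before then.

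The cost is one line in Appendix C, one or two extra rows in a descriptive table, and the disclosure in item 5. The downside is a slightly less specific count, because cellulitis away from the limb would be included, as the list already accepts for other skin and soft tissue infections.

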Appendix D Summary of statistical analyses

EFFICACY ANALYSIS

Endpoint	Analysis population	Primary analysis	Supportive analysis	Subgroup analysis	Other analyses
Primary endpoint					
HbA1c: Change from baseline at Week 26	ITT	ANCOVA (with missing values imputed by the retrieved dropouts & washout imputation method or by control-based copy reference MI under MNAR): Trt, randomization strata (HbA1c, SBP, CKD3 stage) and country as fixed effects, and baseline HbA1c value as a covariate ANCOVA by CKD strata (with missing values imputed by the retrieved dropouts & washout imputation method or by control-based copy reference MI under MNAR): Trt, randomization strata (HbA1c, SBP, CKD3 stage), trt by CKD stage and country as fixed effects, and baseline HbA1c value as a covariate	Tipping point analysis; ANCOVA (with missing values imputed by the retrieved dropouts & washout imputation method or by control-based copy reference MI under MNAR)	Subgroups: race, ethnicity, age group, gender, baseline BMI, baseline HbA1c, baseline SBP, Duration of diabetes, and country	Summary statistics for observed values and changes from baseline by visit. Graphical presentations for mean changes from baseline (\pm SE) and mean values (\pm SE) by visit. By-visit summary and graph excluding measurements after rescue therapy See Section 1.6 for additional planned analyses.
Secondary endpoints					
Continuous: FPG, body weight: Change from Baseline to Week 26; SBP (for patients with baseline SBP \geq 130 mmHg, all patients): Change from Baseline to Week 12;	ITT	ANCOVA (with missing values imputed by the retrieved dropouts & washout imputation method or by control-based copy reference MI under MNAR): Trt, randomization strata (HbA1c, SBP, CKD3 stage) and country as fixed effects, and baseline value as a covariate	No	No	Summary statistics for observed values and changes from baseline by visit. Graphical presentations for mean changes from baseline (\pm SE) and mean values (\pm SE) by visit See Section 1.6 for additional planned analyses.

Statistical Analysis Plan

Version: Final 3.0

Lexicon Pharmaceuticals Protocol No. EFC14837

Date of Issue: 21 November 2019

Covance Study ID:000000155205

Endpoint	Analysis population	Primary analysis	Supportive analysis	Subgroup analysis	Other analyses

UACR (for patients with UACR >30mg/g at baseline): percentage change from baseline to Week 26
					

Categorical: Proportion of patients with HbA1c <7%, <6.5% at Week 26
	
ITT
	
CMH stratified on randomization strata (HbA1c, SBP, CKD3 stage)
	
CMH method stratified on randomization strata (HbA1c / SBP, CKD3 stage): excluding patients with baseline HbA1c values <6.5% (for <6.5% responders) or <7% (for <7% responders) respectively
	
No
	
By-visit summary and graphs of HbA1c responders (<6.5%, <7%)
 
By-visit frequency summary and graphs of HbA1c responders (<6.5%, <7%) excluding patients with baseline HbA1c values <6.5% or <7% respectively
 
See Section 1.6 for additional planned analyses.

Other endpoints					

SBP, DBP, HbA1c, FPG, body weight, eGFR, Cystatin C, UGE, UGCR, Fructosamine, NT-proBNP: Change from baseline
	
ITT
	
Summary statistics for observed values and changes from baseline by visit
	
No
	
No
	
Graphical presentations for mean changes from baseline (±SE) and mean values (±SE) by visit as appropriate

Proportion of patients: with progression to end-stage renal disease, with progression/improvement of UACR categories, with >50% decline in eGFR
	
ITT
	
By-visit frequency summary
	
No
	
No
	
By-visit graphical presentation as appropriate

Statistical Analysis Plan

Version: Final 3.0
Lexicon Pharmaceuticals Protocol No. EFC14837

Date of Issue: 21 November 2019
Covance Study ID:000000155205

Endpoint	Analysis population	Primary analysis	Supportive analysis	Subgroup analysis	Other analyses
Proportion of patients requiring rescue for hyperglycemia	ITT	Summary statistics	No	No	KM plot; List of patients rescued

ITT=intent-to-treat; PP=per-protocol; ANCOVA=analysis of covariance

Statistical Analysis Plan

Version: Final 3.0
Lexicon Pharmaceuticals Protocol No. EFC14837

Date of Issue: 21 November 2019
Covance Study ID:000000155205

SAFETY ANALYSES

Endpoint	Analysis population	Primary analysis	Supportive analysis	Subgroup analysis	Other analyses
Hypoglycemia	Safety	Follow safety guidelines Number (%) of patients with any investigator reported hypoglycemia, severe hypoglycemia, documented symptomatic hypoglycemia during TEAE period, and incidence rates in 100 patient-years.		Severe hypoglycemia or documented symptomatic hypoglycemia by subgroups: race, age group, gender	Severe hypoglycemia or documented symptomatic hypoglycemia: frequency summary of first event/recurrent event by weekly time intervals; frequency summary of any event by hour; KM plot time to first event Documented symptomatic hypoglycemia maybe presented by <54 mg/dL (3.0 mmol/L) as appropriate
Adverse events	Safety	Follow safety guidelines	No	Common TEAEs by subgroups: race, age, gender, baseline SBP, baseline eGFR	To be updated for EOSI
Clinical laboratory data	Safety	Follow safety guidelines	Descriptive	No	No
Vital signs	Safety	Follow safety guidelines	Descriptive	No	No
ECG, Physical examination	Safety	Follow safety guidelines	Frequency summary	No	No

Statistical Analysis Plan

Version: Final 3.0

Lexicon Pharmaceuticals Protocol No. EFC14837

Date of Issue: 21 November 2019

Covance Study ID:000000155205

